STUDY PROTOCOL

Chinese Chronic Liver Failure Consortium Acute-on- Chronic Liver Disease and Failure Study ——a Prospective Multi-center Study in China, the Largest Hepatitis B Virus High-endemic Region

Clinicaltrials.gov ID: NCT02457637

Last updated date: 10 August 2018

OUTLINE

Abbreviations:.....	3
Background	4
Objective	6
Methods	7
Period I Recruitment:	7
Period II 28-Days Hospitalization and Observation:.....	8
Period III Clinic or Telephone Follow-up:	10
Statistical Analysis Plan.....	11
Trial size.....	11
Statistical methods	11
Outcome Measures	12
Primary Outcome Measures:.....	12
Secondary Outcome Measures:	12
Criteria:	14
Inclusion Criteria:.....	14
Exclusion Criteria:	14
Contacts/Locations	16
Reference	17

Abbreviations:

ACLF	Acute-on Chronic Liver Failure
CLIF	Chronic Liver Failure
CLIF-C OFs	Liver-chronic liver failure-Consortium Organ Failure score
HBV	Hepatitis B Virus
CANONIC in Cirrhosis	Chronic Liver Failure (CLIF) Acute-on Chronic Liver Failure
OFs	Organ Failure
AASLD	the America Association for the Study of Liver Disease
AD	Acute Decompensation
SOFA	Sequential Organ Failure Assessment Score
INR	International Normalized Ratio

Background

Acute-on chronic liver failure (ACLF) was first described by Japanese researchers in 1995[1]. In 2011, the American Association for the Study of Liver Disease (AASLD) and the European Association for the Study of the Liver (EASL) concluded that the core characteristics of ACLF were multiple organ failures and high short-term mortality[2]. In 2013, the EASL-CLIF (the European Association for the Study of The Liver-chronic liver failure) established the CLIF-SOFA[3] (chronic liver failure-sequential organ failure assessment) criteria of ACLF through a prospective multicenter study at 29 liver units in eight European countries for 1 year, with a focus on patients with alcoholic cirrhosis with acute decompensation (AD)[4]. In China, patients with acute deterioration of previously chronic liver disease were diagnosed with chronic severe hepatitis, until 2008 these patients had been termed "ACLF", due to the APASL reached a consensus of diagnostic criteria of ACLF[5, 6]. In the Asia-Pacific region, the majority of liver disease is viral hepatitis, while in western countries, it is alcoholic liver disease[7]. There is a sharp east-west divide with respect to the definition of ACLF, especially in the definition of chronic liver disease and its precipitating events[8, 9].

The investigators analyzed 6 years' data of hepatitis B virus (HBV)-related chronic liver disease in patients with AD in two affiliated hospitals of Shanghai Jiao Tong University School of Medicine. These data were also

quantified and sent to the EASL-CLIF center for analysis. 80% of whole patients were clinically diagnosed with cirrhosis, 30% of which had pathological diagnosis. Through analysis of the liver tissues of the liver transplantation (LT) patients, 95% had pseudo-lobules. The residual 5% of liver tissues were in the S3 stage of progressive liver fibrosis[10]. Compared with the CANONIC (EASL-CLIF Acute-on-Chronic Liver Failure in Cirrhosis), there are many similarities between ACLF patients with alcoholic cirrhosis or HBV induced cirrhosis: (1) The age of ACLF patients is younger than that of cirrhotic patients with AD. (2) ACLF is exist at any stage of liver fibrosis. (3) The number of organ failures decides the severity of the disease and is related to mortality of the patient. (4) Predisposition to acute liver injury (ALI) does not correlate with the history of the disease and outcome of the patient. (5) The 90-day mortality rate of ACLF is 45-50%, which is obviously higher than that of non-ACLF patients (5%). (6) Eastern and western types of ACLF can have similar SOFA scores as a diagnostic criterion (CLIF-OF or CLIF-SOFA), and a similar prognostic model to predict the outcomes of ACLF and non-ACLF patients[11]. ACLF patients with cirrhosis induced by HBV or alcoholism differ in main types of organ failure. The former group is liver failure (total bilirubin \geq 12mg/dl) and coagulation failure (international normalized ratio; INR \geq 2.5), whereas the latter group is renal failure (creatinine \geq 2mg/dl or use of renal replacement therapy) and nervous system failure (hepatic encephalopathy; HE \geq III grade)[4, 12].

Research on hepatic pathology in HBV-induced ACLF patients after LT in Renji Hospital demonstrated that the pathological characteristics of ACLF may be MHN/SMHN (massive hepatic necrosis/submassive hepatic necrosis) in the background of liver pseudo-lobules. Regeneration of hepatic progenitor cells, cholestasis, and sepsis are other possible pathological features of ACLF[13].

Objective

The overall objective is to build a prospective multicenter clinical patient cohort representing Eastern-type ACLF in patients with chronic liver disease (cirrhotic and non-cirrhotic) of various etiologies, accompanied by AD or ALI, to characterize disease progression and establish appropriate diagnostic criteria.

Methods

Period I Recruitment:

The investigators plan to enroll 2000-3000 consecutive patients from January to December 2015. The research will be carried out in about 14 Chinese national wide liver centers each of whose total beds are around 500. Only chronic liver disease patients of various etiologies with AD or ALI will be enrolled. Then we will scan all of the enrolled patients and exclude those who fit our exclusion criteria.

Every patient remained will have a unique number. As soon as they are hospitalized, name, age, sex, ID (identification) number, telephone number, e-mail address, WeChat (a popular mobile phone text and voice messaging communication service) number, family address, and degree of education will be collected. The investigators will get the history and etiology of their liver disease, such as hepatitis B, alcoholic liver disease, and autoimmune liver disease. For viral hepatitis, the investigators will ask how antiviral therapy is conducted. The investigators will ascertain if the patients have a history of cirrhosis and for how long. The investigators will ascertain if the patients have any of the following predisposing factors: HBV reactivation, bacterial infection, active alcohol intake, HBV superimposed by other hepatitis viruses, gastrointestinal bleeding, portal vein thrombosis, surgery, intake of hepatotoxic drugs or herbs, or physiological exhaustion. The

investigators will establish the main cause of admission: gastrointestinal bleeding, hepatic encephalopathy, ascites, bacterial infection, jaundice or ALL. The investigators will determine whether the patients have chronic disease such as hypertension, coronary heart disease, diabetes, chronic renal disease, or connective tissue disease.

Period II 28-Days Hospitalization and Observation:

During hospitalization, data will be collected at 1, 4, 7,14, 21 and 28 days (or last visit date, if the patient is hospitalized less than 28 days), and 24h prior to death or LT (if the patient dies or has LT) and focus on the following three aspects.

The first aspect is evaluation of organ failure. The circulatory system will be evaluated by measuring heart rate and blood pressure and use of vasopressors. Renal function will be evaluated by serum creatinine or renal replacement therapy. Coagulation function will be evaluated by INR (international normalized ratio of prothrombin time). Liver function will be evaluated by serum total bilirubin. The respiratory system will be evaluated by the ratio of oxyhemoglobin saturation and fraction of inspired oxygen. The nervous system will be evaluated by the grade of hepatic encephalopathy. Bacterial infection, including pneumonia, urinary tract infection, spontaneous bacterial peritonitis, spontaneous bacteremia, and cellulitis will be evaluated by positive culture results or imaging findings.

Systemic inflammatory reactive syndrome, sepsis, severe sepsis and septic shock will also be assessed. Gastrointestinal bleeding before and after admission, treatment with diuretics, and paracentesis will be recorded. The investigators will establish whether ascites and hepatic encephalopathy can be medically controlled.

The second aspect is laboratory examinations. Tests at admission will include routine blood, urine and stool tests, liver and renal function tests, blood electrolytes, blood-gas analysis, blood glucose, coagulation test, C-reactive protein (CRP), procalcitonin (PCT), HBV antibodies and antigens, anti-hepatitis A (IgM), HBV-DNA, anti-hepatitis E (IgM), anti-hepatitis C, and immunoglobulins (IgA, IgG, IgM and IgM-4). Tests at other times will include blood, urine and stool routine tests, liver and renal function tests, blood electrolytes, blood glucose, coagulation test, CRP and PCT (procalcitonin). Tests optionally done during hospitalization will include autoantibody measurement, blood culture (if the patients have fever and shivering), sputum culture (if there is suspicion of pulmonary infection), middle urine cultivation (when there is suspicion of urinary tract infection) and ascites culture (when there is suspicion of spontaneous bacterial peritonitis).

The third aspect is imaging. During hospitalization, thoracic X ray or computed tomography (CT) will be done to diagnose pulmonary infection. Abdominal CT (enhanced when necessary), B ultrasound and Fibro-Scan or

other elastography will be done to diagnose cirrhosis (or fibrosis), portal thrombosis, esophageal and gastric varices and hepatocellular carcinoma.

Period III Clinic or Telephone Follow-up:

Patients will be followed up regularly after discharge. When the patients die during follow-up, the time of death and main cause of death will be noted.

When the patients undergo LT during follow-up, the time of LT and the results of hepatic pathology will be noted.

Follow-up is by clinical visiting or telephone call depending on whether the patient can attend the clinic. Clinical follow-up is once a month for 2 years adding to 24 visits. The time of visit will be recorded. Antiviral therapy and alcohol intake will be monitored (if the patient has). Laboratory tests include routine blood tests, liver and renal function test, coagulation test, CRP and PCT. B ultrasound will be done to monitor cirrhosis (or fibrosis) and hepatocellular carcinoma. Telephone follow-up will be at 28 days, 3, 6,9, 12, 15, 18, 21 and 24 months. The investigators will determine whether there are new complications (e.g. gastrointestinal bleeding, hepatic encephalopathy, ascites, bacterial infection) and hepatocellular carcinoma.

Statistical Analysis Plan

Trial size

This is an exploratory, observational study, and anticipated size for this study is 2000-3000 patients.

Statistical methods

Refer to the CANONIC study, at the beginning we will focus on (but not limit in) the relationship between 6 parameters (TB, INR, Creatinine, SpO₂/FiO₂, mean arterial pressure and West-Haven grade), one for each organ/system, from CLIF-C OFs and 28-days or 90-days mortality and LT rate. Descriptive statistics, mean and standard difference, will be used to describe continuous variables, and frequency and percent will be to describe categorical variables (such as gender). Statistical significance ($P < 0.05$). In univariate statistical comparisons, the chi-square test will be used for categorical variables, T-test and Mann-Whitney test for continuous variables. Risk ratio (RR) will be used to evaluate and establish the cutoff value for each organ/system. Multivariate logistic regression, Cox' s PH models and other exploratory models would be used in the establishment of our ACLF prognostic scoring systems. The area under the ROC (AUC) will be used to compare the predictive value of ours with others. LT patients will be considered as censored and the survival function would be adjusted for the risk of liver transplantation at each study time point.

Outcome Measures

Primary Outcome Measures:

1. Short Term Mortality & Liver Transplantation Rate

Description: Mortality & Liver Transplantation Rate will be calculated and reported at 28 days, 90 days, 180 days, 1 year, 2 year and 3 years after enrollment. Among them, the 28-day and 90-day mortality rates are the focus of our observation.

Time Frame: up to 3 years.

Secondary Outcome Measures:

2. The appearance and number of organ failure

Description: The appearance and number of organ failure (including liver, coagulation, renal, circulation, brain, respiratory system) will be evaluated and reported at 1, 4, 7, 14, 21 and 28 days (or last visit) during patients' hospitalization.

Time Frame: Up to 28 days.

3. Biochemical Parameters

Description: Serum bilirubin, international normalized ratio, serum creatinine, alanine aminotransferase, aspartate aminotransferase, alkaline phosphatase, γ -Glutamyltransferase, white blood cell count, neutrophil count and hemoglobin will be collected and reported at 1, 4, 7, 14, 21 and 28 days (or last visit) during patients' hospitalization.

Time Frame: Up to 28 days

4. Models for Disease Severity

Description: MELD score, MELD-Na score, CLIF-SOFA score, SOFA score and APACHE scores will be calculated and reported at 1, 4, 7, 14, 21 and 28 days (or last visit) during patients' hospitalization.

Criteria:

Inclusion Criteria:

1. Inpatient (hospitalization >1 days) (including patient in emergency observation wards);
2. Chronic liver disease patients including non-alcoholic fatty liver disease patients, chronic liver hepatitis patients without cirrhosis, compensated cirrhosis patients and decompensated cirrhosis patients;
3. Having acute liver injury [ALT (alanine aminotransferase) > 3NL (normal level), AST (aspartate aminotransferase) > 3NL or TB (total bilirubin) > 2NL within 1 week before enrollment] or acute decompensation [having ascites, hepatic encephalopathy, bacterial infection, gastrointestinal bleeding or jaundice (TB > 5NL) within 1 month].

Exclusion Criteria:

1. pregnancy;
2. hepatocellular carcinoma or other liver malignancies;
3. malignancy of other organs;
4. severe chronic extrahepatic disease including chronic obstructive pulmonary disease combined with respiratory failure, coronary heart disease with cardiac function level 3 (NYHA), myocardial infarction in the 3 months before admission, diabetes with severe complications and chronic kidney disease with end-stage renal failure;

5.receiving immunosuppressive drugs for reasons other than chronic liver disease;

Contacts/Locations

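### The SAP gives centre no role although patients come from about 14 centres; if centres differ, intervals for mortality and LT rates may be too narrow

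*Combined protocol and SAP*

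**What the plan says.** Methods, Period I Recruitment: the study is to run in "about 14 Chinese national wide liver centers", each with around 500 beds. The Objective is a cohort that represents Eastern-type ACLF, used to characterise progression and to set diagnostic criteria.

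Statistical Analysis Plan, Trial size: "This is an exploratory, observational study, and anticipated size for this study is 2000-3000 patients". No precision target, power, event count or intra-centre correlation is given.

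Statistical Analysis Plan, Statistical methods: for univariate comparisons, "the chi-square test will be used for categorical variables, T-test and Mann-Whitney test for continuous variables"; risk ratios set the organ cutoffs; then "Multivariate logistic regression, Cox' s PH models and other exploratory models would be used in the establishment of our ACLF prognostic scoring systems". AUC is used to compare the new score with existing ones. LT patients are censored, with an adjustment of the survival function for LT risk.

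Nowhere in that section does centre appear as covariate, stratum, random effect, frailty, cluster for a robust variance, or unit of validation.

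**The concern.** In their standard form the named tests and models take patients as independent. Patients in one hospital share referral pattern, case mix, care and access to LT, so their outcomes may be correlated.

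Two things follow if they are. First, an ordinary standard error for an overall mortality or LT rate leaves out variation between centres, and that rate is the primary outcome. Second, if a parameter such as bilirubin or INR also differs on average between centres, its estimated effect and cutoff can absorb centre differences that would not hold in another hospital. The second matters because the product is a score and a set of criteria intended for use beyond these sites.

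**Working it through.** **The plan's own figure.** The 2000-3000 patients are stated without inputs, so there is no calculation to reproduce.

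**Inputs.** From the documents: n = 2000 to 3000; about 14 centres; significance at P < 0.05 (two-sided assumed); 90-day mortality 45-50% in ACLF and 5% in non-ACLF (Background). Assumed: ICC, shown at 0 to 0.02; equal centre sizes; centres a sample of hospitals; overall 90-day mortality 15%, used only to express half-widths in points.

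**1. Overall rates.** Average centre size m = 2000/14 = 143 or 3000/14 = 214. Design effect DE = 1 + (m − 1) × ICC; SE multiplier = √DE; effective n = n/DE; 95% half-width = 1.96 × √(0.15 × 0.85/n) × √DE.

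| n | ICC | DE | SE multiplier | Effective n | Half-width (points) |
|---|---|---|---|---|---|
| 2000 | 0 | 1.00 | 1.00 | 2000 | 1.56 |
| 2000 | 0.005 | 1.71 | 1.31 | 1170 | 2.05 |
| 2000 | 0.01 | 2.42 | 1.56 | 827 | 2.43 |
| 2000 | 0.02 | 3.84 | 1.96 | 521 | 3.07 |
| 3000 | 0 | 1.00 | 1.00 | 3000 | 1.28 |
| 3000 | 0.005 | 2.07 | 1.44 | 1452 | 1.84 |
| 3000 | 0.01 | 3.13 | 1.77 | 958 | 2.26 |
| 3000 | 0.02 | 5.27 | 2.29 | 570 | 2.93 |

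At n = 2000 and ICC 0.01, an ordinary 95% interval would cover about 79%. At ICC 0.02, adding 1000 patients in the same centres raises the effective size only from 521 to 570. The documents do not bound the ICC; at 0.05 the multiplier would be 2.84 (n = 2000) to 3.42 (n = 3000).

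**2. Is an ICC in this range plausible?** Take 47.5% and 5% as the ACLF and non-ACLF mortality. An overall 15% then means an ACLF share of (15 − 5)/(47.5 − 5) = 24%. If centres differ only in that share, the between-centre SD of mortality is 0.425 × SD(share), and ICC = SD² / (0.15 × 0.85). For ICC 0.01: √(0.01 × 0.1275) = 0.036, and 0.036/0.425 gives an SD of about 8 points in ACLF share. ICC 0.005 needs about 6 points and 0.02 about 12. The eligibility criteria admit cirrhotic and non-cirrhotic patients of many aetiologies, so such differences are plausible, but the documents hold no data on them.

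**3. Tests of patient-level parameters.** A simulation used 14 equal centres, 15% risk, a predictor with no true effect and 1500 data sets per setting (Monte Carlo SE about 0.6 points). The outcome ICC on the latent logistic scale was 0.02 or 0.05. The centre variance is ICC/(1 − ICC) × π²/3 = 0.067 or 0.173; multiplied by 0.1275 this is roughly 0.009 or 0.022 on the scale used in step 1. Rejection at a nominal 5%, over both n:

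| Predictor ICC | t-test ignoring centre |
|---|---|
| 0 | 5.1-5.7% |
| 0.02 | 5.3-7.1% |
| 0.05 | 5.1-8.9% |
| 0.10 | 5.3-9.7% |
| about 1 (centre-level variable) | 17-41% |

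A within-centre score test stayed at 3.5-5.9% throughout.

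**4. AUC differences.** Their standard errors rest on the same independence assumption, but the multipliers in step 1 are for rates. The size for AUC differences was not computed.

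**The case against.** A reader might infer that the plan has chosen to treat all patients as independent, so that its P values and intervals are certainly too optimistic. The documents do not support that. The SAP is a short list of methods and is silent on centre; its allowance for further exploratory models leaves adjustment open. It specifies no interval for mortality, only rates to be calculated and reported, so no planned interval can be shown to be wrong. The ICC is not in the documents.

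It is also tempting to apply the design effect for rates to every analysis. Step 3 shows that it does not carry over to the six patient-level parameters. Only a variable that is essentially a property of the centre is badly affected, and none of the six is shown to be one. Against a contrast as large as 45-50% versus 5% mortality, a few points of type I error are unlikely to change a conclusion. The study also calls itself exploratory.

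The strongest technical objection concerns the target. If the 14 centres are fixed strata and inference stops there, the variance of the pooled rate is at most p(1 − p)/n, and the ordinary interval is, if anything, slightly conservative. That is correct, but it does not fit the Objective, which reaches beyond the participating hospitals.

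Lastly, the SAP does plan an adjustment for LT risk, so LT is not ignored; what is unstated is whether that adjustment allows for centre.

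These objections limit the size and certainty of the point. They do not supply the missing specification.

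**Conclusion.** The point holds as a conditional omission that should be corrected. The SAP does not say how centre will be handled, while the study aims to generalise from about 14 centres. If centres differ, ordinary intervals for 28- and 90-day mortality and LT rates may be too narrow, with true standard errors about 1.3 to 2.3 times larger. That figure rests on an assumed ICC of 0.005-0.02, equal centre sizes and centres taken as a sample. At ICC 0 there is no effect. Intervals for AUC differences may also be too narrow, by an amount not estimated here.

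For the six parameters the effect on P values is modest, about 5-10% rejection at a nominal 5%. That their effects and cutoffs partly reflect centre differences is possible but not demonstrated. Confidence in the size is medium, because it depends on an ICC that the documents do not supply.

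**What to change.** In Statistical Analysis Plan, Statistical methods, add:

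- **Models.** A centre random intercept in logistic models; for Cox models, a shared frailty or a cluster-robust variance with small-sample correction, with a centre-stratified Cox model as sensitivity analysis. Fixed centre effects or stratified baselines should not be the main form of the score, because they do not transfer directly to a patient from a new hospital.
- **Rates and AUC differences.** Intervals from a centre-level bootstrap or a small-sample-corrected cluster variance. The correction matters with only about 14 clusters.
- **Validation.** Check the score and cutoffs by leaving out one centre at a time, and report the spread across centres.

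The crude univariate tests can stay as descriptive screening; replacing each with a stratified version is a matter of preference.

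The cost is a few SAP sentences, a little more analysis and somewhat wider intervals. The only data needed are each patient's enrolling hospital, which Period I does not list as a field but which should be known.

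### The AUC comparison of the new ACLF score with existing scores has no planned internal validation, so it favours the new score: slightly if the model is pre-specified, materially only if cutoffs searched in the same data enter the score

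*Combined protocol and SAP*

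**What the plan says.** The SAP, under Trial size, states: "This is an exploratory, observational study, and anticipated size for this study is 2000-3000 patients". No power, expected AUC or event count supports that range.

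Under Statistical methods the score is built in steps:

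- Predictors: "at the beginning we will focus on (but not limit in) the relationship between 6 parameters", one for each organ system. The list is therefore open.
- Cutoffs: "Risk ratio (RR) will be used to evaluate and establish the cutoff value for each organ/system". No candidate grid or selection rule is given.
- Model: logistic and Cox regression "and other exploratory models would be used in the establishment of our ACLF prognostic scoring systems".
- Comparison: "The area under the ROC (AUC) will be used to compare the predictive value of ours with others".

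The other scores are not named in that sentence. The likely comparators are those listed under Secondary Outcome Measures, item 4: MELD, MELD-Na, CLIF-SOFA, SOFA and APACHE. The emphasis throughout is on mortality at 28 and 90 days.

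The Background describes an earlier series of HBV-related "chronic liver disease in patients with AD in two affiliated hospitals". It is given no validation role.

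**The concern.** A score evaluated on the patients who supplied its cutoffs, variables and coefficients looks better than it will in new patients. Existing scores have fixed weights and gain no such advantage, so the error falls on one side of the comparison only.

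AUC is the only means the SAP states for judging whether the new score predicts better than the established ones. If much of the building is data-driven, part or all of an apparent gain of a few hundredths could come from fitting alone, and the plan contains nothing that would reveal it.

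**Working it through.** **1. Is validation planned anywhere?** The outline lists two subsections under the SAP, Trial size and Statistical methods, and both are present. Neither mentions a split sample, an external cohort, cross-validation, the bootstrap, shrinkage or an optimism correction. The SAP's reference to the CANONIC study introduces the choice of six parameters and names no validation step.

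**2. Plausible event rates.** The documents do not give the case mix. The Background gives 90-day mortality of 45-50% in ACLF (midpoint 47.5%) and 5% in non-ACLF patients. If those rates applied here:

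- ACLF share = (overall mortality - 0.05) / (0.475 - 0.05)
- At 13% mortality: 0.08 / 0.425 = 0.19
- At 25% mortality: 0.20 / 0.425 = 0.47

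**3. Size of the bias.** The plan has no figure of its own to reproduce, so the size was simulated.

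- Assumptions: n = 2000 or 3000; six normal predictors of graded strength, correlation 0 or 0.3; full-model AUC 0.75 or 0.85; two unfitted comparators (equal-weight continuous, and 0-2 points per organ at fixed cutoffs); truth taken from 60,000 new patients; 100 datasets in each of 32 settings.
- Bias = (apparent new-minus-existing AUC) - (true new-minus-existing AUC).

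| How the score is built | 5% deaths | 13% deaths | 25-48% deaths |
|---|---|---|---|
| Six pre-specified continuous predictors | 0.003-0.015 | 0.001-0.006 | 0.001-0.006 |
| 20 candidates (14 noise) screened at P<0.05 | 0.006-0.025 | 0.002-0.011 | 0.002-0.008 |
| Risk-ratio cutoffs, five candidates each | 0.024-0.050 | 0.012-0.031 | 0.005-0.024 |
| Risk-ratio cutoffs, full 10th-90th percentile search | 0.029-0.077 | 0.014-0.047 | 0.007-0.033 |

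The Monte Carlo standard error is 0.003 or less. The comparators' own apparent-minus-true AUC lay between -0.004 and 0.004, so the bias comes from the fitted score.

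**4. Different assumptions.** A separate simulation used correlated predictors, an existing score with AUC of about 0.80 and a 25-point cutoff grid. Bias at 180 deaths in 2000 (9%), 375 in 2500 (15%) and 660 in 3000 (22%) was:

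- pre-specified six-variable model: 0.006, 0.003, 0.002
- selection from 30 variables: 0.014, 0.007, 0.005
- cutoff search on six variables: 0.030, 0.022, 0.016
- cutoff search plus selection on 30 variables: 0.076, 0.046, 0.033

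The 0.014 quoted as the top of the screening range thus belongs to 30 candidates at 9% deaths.

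**5. Lower event rates.** Deaths by day 28 cannot exceed deaths by day 90. At an assumed 2% rate with n = 2000, two runs gave 0.016 and 0.031 for the continuous model, 0.086 and 0.096 for five-candidate cutoffs, and 0.118 and 0.125 for the full search. One run of screening gave 0.069.

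**6. Does validation remove the bias?** This was tested in 12 settings with 14 centres, 90-day mortality of 5, 13 or 25%, AUC 0.75, zero correlation, assumed centre differences and transplants censored.

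| How the score is built | Bias of apparent difference | After correction |
|---|---|---|
| Continuous, bootstrap | 0.002-0.012 | -0.002 to 0.003 |
| Screened, bootstrap | 0.004-0.024 | -0.009 to -0.001 |
| Full cutoff search, bootstrap | 0.026-0.081 | 0.006 to 0.028 |
| Full cutoff search, seven held-out centre groups | 0.026-0.081 | -0.002 to 0.006 |

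**The case against.** **Cutoffs may never enter the score.** The sentence on cutoffs is separate from the sentence on model building, and the Objective is to establish diagnostic criteria. The cutoffs may serve only to define organ failure. This stands: the material tier is conditional.

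**Screening variables is not a serious problem at this size.** A reader might infer that any data-driven choice is materially harmful. At 13% deaths or more the figures for screening alone overlap those of the pre-specified model or lie little above them, so that reading is not supported.

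**The simulated predictors are idealised.** West-Haven grade is ordinal and cannot be searched over percentiles. Making one predictor five-level (assumed shares) cut the bias at 13% from 0.048 to 0.032 for the full search and from 0.034 to 0.017 for five candidates; at 5% there was no reduction. The third decimal should not be relied on.

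**The study is exploratory.** No test of an AUC difference is stated, AUC is not a listed outcome, and saying nothing about validation is not a commitment to report the apparent AUC alone. This lowers the stakes. It does not change the direction of the bias if the plan is followed as written.

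**A cohort of 2000-3000 is large enough.** That holds for a pre-specified continuous model at 13% deaths or more. It does not hold for searched cutoffs.

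**Conclusion.** The concern holds in a graded form, and the point is worth fixing. As written, the comparison favours the new score. At about 13% deaths the bias is small for six pre-specified continuous predictors (about 0.001-0.006), modest for screening alone (about 0.002-0.014, depending on the number of candidates) and material (about 0.01-0.05) only if cutoffs are searched in these data and enter the score. All sizes rest on assumed effects, comparators, cutoff rules and case mix.

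Two stronger readings are not supported:

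- **That the new score would falsely outrank the named scores.** In one setting, five-candidate cutoffs gave +0.020 apparent against -0.010 true when compared with an assumed categorised score, but -0.019 against -0.049 when compared with an assumed continuous one. The sign depends on the comparator, and the named scores were not simulated.
- **That the 5% column is a worst case.** It corresponds to no ACLF patients only under the Background's 90-day rates. Mortality at 28 days may be lower, and the documents give none for some eligible groups, such as patients with non-alcoholic fatty liver disease.

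The primary mortality and transplantation outcome is unaffected.

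**What to change.** Add after the AUC sentence in Statistical methods:

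> The AUC of the new score at 28 and 90 days, and its difference from each existing score, will be reported after internal validation that repeats every building step (cutoff choice, variable selection and model fitting), and not as the apparent AUC alone. If cutoffs are searched, cross-validation leaving out groups of centres will be used, with new and existing scores compared in the omitted patients and the results pooled.

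The second sentence is there because the bootstrap alone left 0.006-0.028 after a full cutoff search. That rests on one set of assumptions; the five-candidate rule was not tested under centre-grouped cross-validation, nor was cutoff search combined with variable selection.

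The cost is SAP wording and computing time, with no new data. There are four drawbacks:

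- Building steps must be written as repeatable rules, which limits free exploration. Recruitment was planned for 2015 and the document is dated August 2018, so it is unknown whether this can still precede building the score.
- The reported advantage of the new score will be somewhat smaller.
- With screened variables the bootstrap may over-correct slightly (by up to 0.009 in the test).
- Centres need grouping. With about 14 centres in seven groups and 2000 patients, deaths per group are about 2000 × 0.05 / 7 = 14 at 5% mortality and 2000 × 0.13 / 7 = 37 at 13%, before any loss to transplantation. Only the pooled result should be interpreted.
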